**Study withdrawal/ Discontinuation:**

The subject can withdraw the consent any time during the study. The PI or the Sub I can withdraw the subject if they feel that subject safety may be affected by the participation of that subject.

**Data Analysis**

The CNAPs are visually analyzed and given a score based on their amplitude. Mean values for each level of stimulation are then determined. A comparison between the baseline value (SHAM stimulation) and the amplitude at each level of stimulation is then determined. The amplitudes of the various nerve fibers at each level of stimulation are also examined to determine if a particular nerve fiber is particularly susceptible to stimulation of the ABVN. Statistical analysis is performed using analysis of variance (ANOVA).

The blood samples will be sent as deidentified to Purdue lab for processing and data will be analyzed by the Purdue team.

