### **Technique of transcutaneous auricular vagus nerve stimulation**

Two electrodes are placed in the auricle of the left ear at loci described by the (1) the cyma concha and (2) the slope between the antihelix and cavum concha (Figs. A and B).

These locations are chosen based on auricular sub regions with the greatest probability of vagal innervation of the human auricle, as has been previously determined by cadaver dissection (9) Electrodes are passed through the penetration panel with inline low-pass radio frequency filtering (80 MHz). Electrical stimulation to these electrodes is provided by a constant-current stimulator with 100 V compliance (FE 180 Stimulus Isolator, AD Instruments, Boston MA).

Stimuli consist of rectangular pulses with 450  $\mu$ s pulse width, delivered at 30 Hz, and pulse train duration of 0.5 seconds, as previously described in studies of chronic pain patients (10). Stimulation is gated, with 0.5-second delay, after peak inhalation (i.e., during exhalation) or after peak exhalation (i.e., during inhalation).

Respiratory gating for stimulation requires real-time evaluation of the respiratory cycle. We use a respiratory belt transducer designed to measure changes in chest diameter resulting from breathing (Fig. C). This pneumatic belt is placed around the subject's lower thorax at the level of maximum respiratory expansion (TN 1132/ST Respiratory Belt, AD Instruments, Boston MA). The belt is pretensioned slightly. The belt contains a capacitive sensing element and custom electronics that respond linearly to changes in length. The transducer is connected to a PowerLab pod port (Power Lab, AD Instruments, Boston MA). The transducer contains a flexible sensing element bonded to the inside of the fabric belt.

Once electrode placement in the ear is validated, subjects are asked to rate stimulation intensity of 0 to 10 (0: no sensation, 10: mild discomfort). Current intensity is set to achieve moderate to strong (but not painful) sensation (target score: 4/10), and this current intensity is used on subsequent stimulation runs. For SHAM baseline study, the electrode in the ear remains in place, but the leads are disconnected from the stimulator.

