#### ABVN Phase 2 Outcome Measures/Endpoints

1. To measure the amplitude of vagal nerve compound action potentials in gastroparetic subjects with symptoms of nausea and vomiting with skin electrodes over right and left vagus nerve during ABVN stimulation and also during the vagal maneuvers phase
2. To measure respiratory changes in heart rate during ABVN and also during the vagal maneuvers phase.
3. To measure changes in the amplitude of the surface electrogastrogram during ABVN and also during the vagal maneuvers phase.
4. To measure the Heart rate variability(HRV), vagal nerve compound action potentials and electrogastrogram in subjects undergoing VNS Therapy for focal or partial seizures.
5. To measure the effect of ABVN stimulation on the gastric hormones in healthy and gastroparetic subjects.
6. To see the effect on the data if we change the regular ECG electrodes to MEA electrodes in the neck.
7. To see the effect of COVID 19 on HRV in healthy volunteers diagnosed with COVID-19

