#### **EAR STIMULATION GROUP:**

This is a onetime visit only that involves baseline and test procedures.

1. Two MRI compatible electrodes will be placed in the auricle of the left ear, fixed by a plastic armature that wraps around the ear. The leads from the electrodes are connected to a stimulator.
2. A pneumatic belt may be placed around the lower thorax. Pneumatic tubes connect this belt to a pressure transducer that in turn sends signal to a laptop-controlled device that acquires the signals.

3. Two ECG electrodes are placed on both sides of the neck overlying the area near the carotid artery where the vagus nerve is superficial. This is to measure the vagal action potentials in the neck.
4. Two ECG electrodes are placed one on each arm and one on the chest for measurement of the electrocardiogram (ECG)
5. Three ECG electrodes are placed on the abdomen in a line parallel to the longitudinal axis of the stomach to record the electrogastrogram (EGG).

Electrical stimulation of the electrodes placed in the ear is provided by a current-constant stimulator. The stimuli consist of rectangular pulses with  $450\text{ }\mu\text{s}$  pulse width, delivered at 30 Hz, and pulse train duration of 0.5 seconds. Stimulation is gated, with 0.5-second delay, after peak inhalation (i.e., during exhalation) or after peak exhalation (i.e., during inhalation).

Baseline procedure:

A butterfly catheter is inserted under aseptic conditions into a peripheral vein. Fifteen ml (1 tablespoon) of blood is withdrawn and placed on ice. After this the baseline recording will be started as described below.

During the baseline recording the stimulating electrodes are placed in the auricle of the subject but no current is delivered. Cervical neck electrodes are placed over the right and left vagus nerve to record any electrical activity that might occur during the baseline period. Baseline ECG and EGG recordings are also performed during this interval.

Test procedure:

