**EAR STIMULATION GROUP:**

This is a onetime visit only that involves baseline and test procedures.

1. Two MRI compatible electrodes will be placed in the auricle of the left ear, fixed by a plastic armature that wraps around the ear. The leads from the electrodes are connected to a stimulator.
2. A pneumatic belt may be placed around the lower thorax. Pneumatic tubes connect this belt to a pressure transducer that in turn sends signal to a laptop-controlled device that acquires the signals.
3. Two ECG electrodes are placed on both sides of the neck overlying the area near the carotid artery where the vagus nerve is superficial. This is to measure the vagal action potentials in the neck.
4. Two ECG electrodes are placed one on each arm and one on the chest for measurement of the electrocardiogram (ECG)
5. Three ECG electrodes are placed on the abdomen in a line parallel to the longitudinal axis of the stomach to record the electrogastrogram (EGG).

Electrical stimulation of the electrodes placed in the ear is provided by a current-constant stimulator. The stimuli consist of rectangular pulses with 450  $\mu$ s pulse width, delivered at 30 Hz, and pulse train duration of 0.5 seconds. Stimulation is gated, with 0.5-second delay, after peak inhalation (i.e., during exhalation) or after peak exhalation (i.e., during inhalation).

Baseline procedure:

A butterfly catheter is inserted under aseptic conditions into a peripheral vein. Fifteen ml (1 tablespoon) of blood is withdrawn and placed on ice. After this the baseline recording will be started as described below.

During the baseline recording the stimulating electrodes are placed in the auricle of the subject but no current is delivered. Cervical neck electrodes are placed over the right and left vagus nerve to record any electrical activity that might occur during the baseline period. Baseline ECG and EGG recordings are also performed during this interval.

Test procedure:

Stimuli consisting of rectangular pulses with 450  $\mu$ s pulse width, delivered at 30 Hz, and pulse train duration of 0.5 seconds are then delivered to the subject. Current intensity is set to achieve moderate to strong (but not painful) sensation, and pulse frequency/duration is set following pilot testing to achieve a subjectively comfortable stimulus sensation. This is 4/10 and is designated “100 per cent.” The current amplitude

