**PI: [name] Effect of Electrical Stimulation of the Auricular Branch of the Vagus Nerve on Cervical Vagus Nerve Compound Action Potentials**

is then increased again by 10 per cent and ABVN is applied again for 60 seconds. This sequence is repeated until the “100 percent” level (4/10) is reached. These stimuli are delivered during expiratory phase of respiration as investigations have shown this to be most effective in producing vagal stimulation (8).

Once the target stimulus intensity has been achieved, stimuli are delivered during the expiratory phase for a total of two minutes. Another 15 ml (1 tablespoon) of blood will be collected 20 minutes after stopping the stimulus.

The subject will be allowed to keep on resting and 20 minutes after the second blood draw, another 15 ml (1 tablespoon) of blood will be drawn. This is the final draw. The catheter will then be withdrawn

The subject will then undergo stimulation at the “100 percent” designated level for 2 minutes and a 5-minute post stimulation recording may be made. This will be followed by another 2-minute stimulation followed by 5 minute of post stimulation recording.

At the end of the 5-minute post stimulation recording. The subject will be allowed to go home

ECG and EGG recordings will be continued during auricular branch vagal nerve stimulation.

If the blood collection is not possible due to any reasons the subjects will still go ahead with the auricular branch stimulation of 2 minutes and 5 minutes recording made after that.

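### Ear-stimulation part of Endpoint 1: CNAPs are scored by eye against a no-current sham, with neither coded reading nor a rule to separate stimulus pickup from nerve response

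*Protocol*

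**What the plan says.** The first item under ABVN Phase 2 Outcome Measures/Endpoints is "To measure the amplitude of vagal nerve compound action potentials in gastroparetic subjects with symptoms of nausea and vomiting", recorded from skin electrodes over both vagus nerves during stimulation of the auricular branch of the vagus nerve (ABVN) and during vagal maneuvers. This point concerns the ear-stimulation part only.

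The Data Analysis section fixes three things:

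- Reading: "The CNAPs are visually analyzed and given a score based on their amplitude".
- Contrast: "A comparison between the baseline value (SHAM stimulation) and the amplitude at each level of stimulation is then determined", tested by ANOVA.
- Fibres: "The amplitudes of the various nerve fibers at each level of stimulation are also examined", to see whether one type is especially susceptible.

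Two places describe the comparator. The technique section says that for sham "the electrode in the ear remains in place, but the leads are disconnected from the stimulator". The ear-stimulation procedures, for healthy and for gastroparetic subjects, say "During the baseline recording the stimulating electrodes are placed in the auricle of the subject but no current is delivered". Under either description there is no stimulus current. In both procedures the baseline precedes the test procedure, in which the current "is then increased again by 10 per cent and ABVN is applied again for 60 seconds".

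For recording details, the section on measuring CNAPs and the electrogastrogram refers to another protocol, in patients with implanted gastric stimulators. Appendix 3 names the previously approved ear-stimulation protocol in healthy volunteers. Neither is reproduced in the text at hand.

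**The concern.** Whether ear stimulation produces CNAPs in the neck is the question in the study's title and in its objectives. The planned answer is a within-subject comparison of eye-assigned scores, with and without current. The two conditions differ in more than the nerve's response. A stimulated trace may also contain the stimulus itself, conducted to the neck skin electrodes. A reader who knows which trace is which may also score it differently.

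The protocol gives no coding of traces for the reader, and no artefact rule for the neck recording. The only filter it mentions is a radio-frequency filter on the stimulating leads, which is not such a rule. At stake is the meaning of a positive result: a rise over sham would have three candidate explanations and no planned way to choose among them. A negative result is not immune either, since a large artefact could hide a response.

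**Working it through.** The protocol gives no effect size, variance or artefact size, so there is no stated figure to reproduce and no bias to compute. The check sets the two conditions side by side.

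**Inputs**

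- Site: stimulation in the left ear; recording from skin electrodes on both sides of the neck (ear-stimulation procedures).
- Waveform: 450 µs rectangular pulses, "delivered at 30 Hz, and pulse train duration of 0.5 seconds".
- Current: starts at 0.1 mA, at most 5.0 mA (stated for healthy subjects only).
- Order: baseline first, then rising current.

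**Stimulus arithmetic**

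- Pulses per train: 30 × 0.5 = 15.
- Spacing: 1000 / 30 = 33.3 ms.
- Share of the train occupied by the pulses themselves: 0.45 / 33.3 = 0.0135, or about 1.4%.
- Largest ratio of currents: 5.0 / 0.1 = 50.

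The pulses are brief and regular. An exclusion interval around each one is therefore practicable if pulse times were stored. Any artefact may outlast the pulse, so 1.4% is a lower bound on what would be excluded.

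**Conditions compared**

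| | Sham | Stimulated |
|---|---|---|
| Ear current | none | present |
| Nerve response to ear pulses possible | no | yes |
| Pickup of ear pulses possible | no | yes |
| Place in session | first | later, current rising |
| Coding of traces for the reader | not stated | not stated |

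**What the contrast estimates**

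Write the mean difference from sham as D = R + P + E, where R is the nerve response, P the pickup and E the reader's expectation. The plan observes D alone.

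1. More subjects estimate D more precisely but do not split it.
2. A rise across levels does not split it either: R and P would both be expected to grow with current.
3. P need not be positive. An artefact that obscures the trace could lower the score.

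**Recordings without current**

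The gastroparetic procedure includes 5-minute recordings after stimulation, the first of them optional. These cannot contain ear pulses, but they show after-effects, whereas the endpoint concerns amplitude during stimulation.

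**The case against.** The strongest objection is that reading and artefact rules usually sit in an analysis plan or reading manual, and none is at hand. Silence on such detail alone would be no finding. What remains is that the protocol itself chose eye scoring and a no-current comparator, and that choice leaves the title question open to other explanations.

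A rule may also already exist. The Appendix 3 protocol asks the same ear-stimulation question and is the likeliest place; the gastric-stimulator protocol is another. This stands: one can say only that this protocol does not state a rule.

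A reader might infer several stronger claims that the document does not support:

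- *That pickup occurs, or that a positive result would be false.* Nothing shows that pickup is present, how large it is or which way it acts. False-positive rates could be produced only from an assumed shift, so none is given.
- *That the scoring is known to be unmasked.* The protocol is silent on coding. Monthly data review by the study team does not say who scores traces. The remark on low signal-to-noise concerns gastric stimulation.
- *That conduction speeds dictate a latency window.* No ear-to-neck path length is given, and the Background describes auricular afferents relaying through brainstem nuclei. A relayed response need not be tightly locked to each pulse.
- *That vagal maneuvers are affected too.* No ear current is applied there.

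Finally, identical processing does not guarantee removal of artefact that outlasts the excluded interval. That stands as a limit of the remedy.

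**Conclusion.** The point holds for the ear-stimulation part of the first outcome measure. As written, the plan cannot by itself attribute a rise over sham to the vagus nerve, because stimulus pickup or reader expectation could produce the same rise. The existence, size and direction of any bias are unknown. The conclusion rests on the no-current sham, the fixed order, scoring by eye, and the absence from this protocol of coded reading and of a pickup rule. It would weaken or fall away if a protocol or analysis plan not shown already supplies these for ear stimulation. This is a cheap improvement to a stated method, not evidence that the study's results would be wrong.

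**What to change.** Amend the Data Analysis section, for ear stimulation only:

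1. Make the analysed variable the CNAP amplitude measured from the digital recording, by a rule fixed before this study's stimulated traces are read. If they have already been read, fix the rule on sham or earlier-study recordings and say so. If either referenced protocol has a rule that covers ear stimulation, cite it instead.
2. Process sham and stimulated recordings identically: the same artefact-exclusion interval around pulse times, placed at matching times in the sham trace, and the same measurement window. Report that activity inside the excluded interval cannot be assessed. This matters for the fibre comparison too.
3. Do any visual scoring on these processed segments, coded so that subject, order and level are hidden.
4. If pulse timing was not stored, do the coded reading only and state that pickup cannot be excluded.

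Where made, the current-free post-stimulation recordings can serve as a supportive check of after-effects only.

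Cost: revised wording, an extraction script and a file-coding step, with no new recordings, subjects or staff. The downsides are analyst time and possible loss of short-latency activity in the excluded interval.

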**Appendix 3: Previously approved protocol for healthy volunteers**

**EFFECT OF ELECTRICAL STIMULATION OF THE AURICULAR BRANCH OF THE VAGUS NERVE ON CERVICAL VAGUS NERVE COMPOUND ACTION POTENTIALS: 1809683671**

**Appendix 4: Previously approved study to use MEA electrodes: 1907095542**

High Resolution, Noninvasive Measurement and Functional Classification of Vagal Nerve Response Patterns in Relation to Gastroparesis Symptom Management using Gastric Electrical Stimulation Therapy
